Assess the effects of the intervention strategies when delivered “all-in” versus “add-in” by measuring the following outcomes.

- Dispersion: Via EHR extraction- Proportion of children over 2 months of age who have NBS/SCT newly documented (as above).
- Knowledge: Caregiver survey- Proportion of caregivers who accurately reported their child's NBS result.
- Inequities in documentation: Via chart review. Demographic data for each infant: primary care site, sex, race, ethnicity, and insurance type.
- Satisfaction: Caregiver survey.

INVESTIGATIONAL PLAN: Overview

General Schema of Study Design

A two-arm, randomized, interrupted time series design will compare an “all-in” and “add-in” approach. In the “all-in” arm, participants receive all toolkit components at once. In the “add-in” arm, participants will have “multiple interruptions” with sequential addition of components in 6 week increments (**Figure – replace 3 month label with 6 week label**). This will allow for exploration of the added benefit of certain components as compared to the whole toolkit.

Toolkit Components:

- 1) Intervention A: EHR “nudge” within the birth history and/or well-child progress note template
- 2) Intervention B: “lunch-and-learn” sessions (in person or pre-recorded per office preference)
- 3) Intervention C: written educational materials (i.e. post cards, poster, PDF files) to alert PCPs to the importance of SCT documentation and “talking points” to facilitate disclosure;

Duration of Study Participation

Duration of study participation for a site will last a total of approximately 5 months. During the 5 months, PCPs will participate in 4 surveys (15 minutes each) and 1 qualitative interview (30 minutes). Study duration of caregivers will be for survey completion (5-10 minutes).

Total Number of Study Sites/Total Number of Subjects Projected

- 1) Sites: At least 2 sites per arm of the study with at least 10 PCPs in each arm are required.
- 2) PCPs: All PCPs from a given office will be eligible for participation. This will result in at least 20 Nemours PCPs at 4 or more office locations in the Delaware Valley. PCP offices will be purposively chosen to include a wide racial distribution within their patients.
- 3) Caregivers: 500 caregivers of infants with SCT or a normal NBS who are cared for within the specified office location.

Study Population

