PCP Implementation Surveys: PCPs will receive surveys by email (through REDCap) every 6 weeks. Survey is expected to take 15 minutes to complete. For PCPs in the “all-in” arm, the first survey will be sent prior to the intervention “roll-out” and every 6 weeks after that. For PCPs in the “add-in” arm, the first survey will be sent prior to intervention A “roll-out”, intervention B “roll-out”, intervention C “roll-out”, and then 6 weeks after. The survey is created specifically for this study and focused on the acceptability of using the intervention component, feasibility of using the intervention component, the opportunity costs of using the intervention component (the time it takes to use the intervention, the perceived effect on other discussion topics with well child visits), and the intention and confidence (i.e. self-efficacy) to document and discuss NBS and SCT results.

PCP Qualitative Interviews: At completion of the Intervention period, PCP participants will be contacted to schedule the qualitative interview. Interviews will be expected to last ~30 minutes. Interviews will be completed over the telephone or using a video conferencing platform. If video conferencing is used, participants will be instructed to keep their camera turned off, so their image will not be recorded. The participant will be notified verbally when the recording has started and when it has stopped.

The qualitative interviews will assess their experience with the components and intention to document and disclose NBS/SCT results in the future.

Infant Identification:

Infants seen at a participating site during the retrospective and intervention period for a well child visit before 2 months of age will be identified through EHR data extraction on a rolling basis (i.e. once a month during the trial) based on ICD10 code for a new patient/well child exam (ICD 10: Z00.110, Z00.111, Z00.121, Z00.129, Z00.00, Z00.01 or CPT: 99381, 99382, 99383, 99384, 99385, 99391, 99392, 99393, 99394, 99395).

Documentation and Discussion of NBS/SCT results for all infants identified: via chart review. For each infant identified, the following data will be collected via EHR extraction and manual chart review:

- Email
- Preferred language
- MRN (to facilitate manual chart review)
- Gender
- Race, ethnicity
- Insurance
- Zipcode (to assess Childhood Opportunity Index)
- Phase of study they were first seen for a WCC (retrospective, “all-in” A/B/C, Intervention A, Intervention B, Intervention C)

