- Presence/absence of NBS
- Result of hemoglobinopathy NBS
- Presence/absence of NBS result documented in 1) problem list, 2) medical history, 3) progress notes
- Presence/absence of a disclosure conversation about NBS result in progress notes (including topics discussed: inheritance patterns, medical implications, reproductive implications, hematology/genetics consultation)
- Presence/absence of NBS results in After Visit Summary communication

Caregiver Survey from retrospective period:

Caregivers of three groups of infants will be surveyed if they are identified as speaking English (through EHR demographic data) and with an email address in the EHR:

- Group 1: All infants with SCT seen before 2 months of age within the 6 month retrospective period
- Group 2: All infants identified as Black or Hispanic seen before 2 months of age within the 6 month retrospective period

- Group 3: Infants seen before 2 months of age within the 3 month retrospective period and not included in group 1 or 2

Caregiver Survey during Intervention Period:

Caregivers from the participating office locations of three groups of infants will be surveyed if they are identified as speaking English (through EHR demographic data) and with an email address in the EHR:

- Group 1: All infants with SCT
- Group 2: All infants identified as Black or Hispanic
- Group 3: Infants seen in the first half of the month and not included in group 1 or 2

Caregivers will receive a survey at 2 and 6 months of age (+/- 1 month) delivered by email (through REDCap). Survey is expected to take less than 10 minutes to complete. Consent and survey responses will be obtained electronically. The survey will inquire about results of the NBS, preferences for information receipt, and satisfaction with well child visit.

Recruitment of Participants

- **See site selection under Study Procedures**

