Sample Size Justification: This is a pilot study and there is no reported effect size on the intervention of this study in the literature. Therefore, the main goal of this study is to explore reliable effect size that would assist designing future studies with formal hypothesis testing. The primary aim of the study is to increase PCP's EHR documentation and disclosure of NBS and SCT carrier results during infancy (age less than 1 month). It has been found in a chart review that 71% of newborns over the last 3 years had a newborn screen result scanned into their chart. The goal of this study is to raise this to 90%. A sample size of 74 in each of the pre- and post-intervention period can detect the targeted difference in newborn screen of 19% with 86% power at the level of significance of 0.05. PCP documentation has been reported as 20% in the literature. We aim to raise this 50%. Again, a sample size of 43 in each of the pre- and post-intervention period would be adequate to detect the targeted difference in the PCP documentation with a power of 85% at the level of significance of 0.05. Currently 53% sickle cell traits has been documented. Once again, the goal is to raise this to 90%. A sample size of 21 infants with sickle cell traits (SCT) in each of pre- and post-intervention periods would be adequate to detect this difference in this documentation with a power of 80% at the level of significance of 0.05. In DE, the prevalence of SCT is 2.1% in overall children and about 7% in African Americans. Considering 2.1% SCT in overall children, we need 1000 infants to screen in each of the pre-and post-intervention periods, to detect the targeted difference with a power of 80% at the level of significance of 0.05. The study plans to recruit 10 PCPs in each of the intervention arm (20 PCP in both arms). About 6-10 infants are expected to be seen by a PCP in a month and 54-90 new infants are expected to be seen by a physician during 9 months of post intervention period. We expect that minimum of $540 \times 2 = 1080$ patients (540 for each intervention) to be seen by 20 PCPs. Therefore, a minimum sample size of 1080 infants is planned for each of the pre-and post-intervention periods for this study. The planned minimum sample size of 1080 in the post intervention period would also be adequate to determine the effect size for survey results and documentation and disclosures for each intervention arm separately.

Analysis of Qualitative Data:

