This project is not greater than minimal risk. There is no physical risk to the PCP, study staff, or caregiver participant in the surveys or interviews. The knowledge gained through the interviews and surveys will help assure we are providing NBS and SCT results in ways PCPs and caregivers prefer. The major risk to this study is the discussion of sensitive subject matter. We will conduct interviews virtually via telephone or Teams at a time that is convenient to the participant. In addition, each interview script will be reviewed by the Stakeholder groups to minimize any confrontational or judgmental terminology and assess for face validity and comprehension.

Since the study procedures are not greater than minimal risk, significant adverse events (SAE) are not expected. If any unanticipated problems related to the research involving risks to subjects or others happen during the course of this study (including SAEs) these will be reported to the IRB in accordance with Nemours IRB policies. AEs that are not serious but that are notable and could involve risks to subjects will be summarized in narrative or other format and submitted to the IRB at the time of continuing review.

Potential Benefits of Study Participation

The PCPs within the implementation science pilot trial may receive the following direct benefits: improved knowledge of the importance of NBS and SCT results, enhanced self-efficacy (i.e. confidence) in the disclosure of NBS and SCT results to their patients, improved rates of documentation of NBS and SCT results. If the implementation strategies are found to be acceptable, feasible, and enhance penetration of NBS and SCT result documentation and disclosure they will be further tested within a multi-site implementation trial.

The caregiver participants may not receive any direct benefit to completing the survey. They may receive direct benefit because their PCP is a participant since they may receive additional education from their PCP regarding their child's NBS results. Results from the caregiver participants will help to improve the delivery of care for others in the future.

Payment to Subjects/Families

All compensation will be provided via Greenphire gift card: Name, address, and date of birth will be required to facilitate gift cards.

- Primary Care Provider (PCP) Survey Incentives (1 every 6 weeks during the intervention phase x 4). \$25 per survey. An additional \$25 if all four surveys are completed.

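### The sample size counts infants over 9 post-intervention months, but sites take part for about 5; with 20 PCPs the planned 1080 infants are not reached and SCT power falls below 80% at the minimum rate

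*Combined protocol and SAP*

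**What the plan says.** The Sample Size Justification assumes 20 PCPs (10 per arm), each seeing 6 to 10 infants a month, and states that "54-90 new infants are expected to be seen by a physician during 9 months of post intervention period". From this it takes 540 infants per arm, 1080 in total, as the minimum for both the pre- and the post-intervention period. It says that 1000 infants per period are needed to find 21 with SCT at 2.1% prevalence, and that 21 per period give 80% power to detect a rise in SCT documentation from 53% to 90%.

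Other sections describe a shorter study:

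- Duration of Study Participation: "Duration of study participation for a site will last a total of approximately 5 months".
- General Schema of Study Design: the add-in arm proceeds "with sequential addition of components in 6 week increments", with three components.
- Payment to Subjects/Families: PCP surveys are "1 every 6 weeks during the intervention phase x 4".
- Infant Identification: infants come from the retrospective and intervention periods only. The item "Phase of study they were first seen for a WCC" lists no phase after Intervention C.

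The pre-period for the primary endpoint has no stated length. Retrospective lengths appear only for the caregiver survey: group 1 is "All infants with SCT seen before 2 months of age within the 6 month retrospective period", group 2 has the same 6 months, and group 3 is "Infants seen before 2 months of age within the 3 month retrospective period and not included in group 1 or 2".

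**The concern.** The infant count is proportional to the length of the window, so 5 months in place of 9 removes four ninths of the post-period sample. Most of the plan can absorb that loss, but the SCT comparison cannot. It is the only calculation that needs about 1000 infants per period, and its margin is thin: 1080 infants yield 22.7 with SCT against 21 required. SCT documentation is part of the primary endpoint (penetration).

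The missing extraction windows are a problem in themselves. From the current text, two analysts could extract records for different pre- and post-periods and both claim to follow the protocol. The plan also says that 1080 post-period infants suffice to estimate effects in each arm separately, and that statement rests on the same 9 months.

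**Working it through.** **Inputs.** From the Sample Size Justification: 20 PCPs; 6 to 10 infants per PCP per month; 9 months; SCT prevalence 2.1%; documentation 53% before and 90% after; alpha 0.05. Statistical Methods makes tests two-sided. Duration of Study Participation gives 5 months. A 6-month pre-period is my assumption, borrowed from the caregiver survey.

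**Reproducing the plan.**

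- Infants: 6 × 20 × 9 = 1080, or 540 per arm.
- SCT infants needed: 1000 × 0.021 = 21.
- Power, arcsine approximation: Φ(h·√(n₁n₂/(n₁+n₂)) − 1.96), with h = 2·asin√0.90 − 2·asin√0.53 = 0.867. For 21 versus 21: Φ(0.867 × √10.5 − 1.96) = 80.2%, matching the stated 80%.
- Other methods at 21 versus 21: pooled z 78%, exact power of the chi-square test 81%, unpooled z 83%, Fisher 69%.

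**Post-period of 5 months, 20 PCPs.**

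- Minimum rate: 6 × 20 × 5 = 600 infants (300 per arm), and 600 × 0.021 = 12.6 with SCT (6.3 per arm, against 540 × 0.021 = 11.3 in the plan).
- Maximum rate: 10 × 20 × 5 = 1000 infants (500 per arm), and 21.0 with SCT.

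**Power, 53% versus 90%, with a 6-month pre-period (assumed) and a 5-month post-period.** SCT counts are rounded to whole infants.

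| Infants per PCP per month | SCT pre vs post | Arcsine | Pooled z | Exact chi-square | Unpooled z | Fisher |
|---|---|---|---|---|---|---|
| 6 | 15 vs 13 | 63% | 58% | 66% | 67% | 52% |
| 7 | 18 vs 15 | 70% | 65% | 66% | 75% | 64% |
| 8 | 20 vs 17 | 75% | 71% | 72% | 79% | 69% |
| 9 | 23 vs 19 | 80% | 77% | 78% | 84% | 72% |
| 10 | 25 vs 21 | 83% | 81% | 82% | 87% | 77% |

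**Pre-period extended to 1080 infants, post-period at 6 per month (23 vs 13).** Arcsine 71%, pooled 64%, exact chi-square 67%, unpooled 79%, Fisher 61%. A longer look-back alone does not restore 80% here under any of the five methods.

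**What would close the gap.**

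- PCPs for 1080 infants in 5 months: 1080/30 = 36 at 6 per month, or 1080/50 = 21.6, so 22, at 10 per month. For 1000 infants: 34 and 20.
- Prevalence (assumed values; 720 pre and 600 post infants, unrounded counts): 3.0% gives 78% arcsine, 74% pooled and 82% unpooled; 3.5% gives 84%, 81% and 87%.

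**If the post-period is exactly 18 weeks** (four surveys, three 6-week intervals): 18 × 12/52 = 4.15 months, giving 498 to 831 infants and 10.5 to 17.4 with SCT.

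**The case against.** Five months may describe the active involvement of sites and PCPs, with record extraction continuing afterwards. The next sentence in that section concerns PCP surveys and interviews, and extraction needs no site activity. The phase list does not exclude this, since Intervention C has no stated end date and a later infant could be coded to it. The caregiver lottery at 4-month intervals and the surveys at 6 months of age also point to activity beyond 5 months. This part has some force: the documents do not fix when extraction ends. But nothing in them states a 9-month window outside the sample size text, and identification is tied to the intervention period. Even 8 months, the most that the lottery timing suggests, gives 6 × 20 × 8 = 960 infants, still below 1080.

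The counts may also be conservative. The requirement reads "At least 2 sites per arm of the study with at least 10 PCPs in each arm are required", so 20 is a floor. Infants are identified by site, so those seen by non-consenting PCPs would count too. Offices chosen for racial distribution may exceed 2.1% SCT, since the plan gives about 7% in African Americans. All this is fair, and it means that 600 is not a forecast. It does not rescue the stated minimum, which is computed from 20 PCPs and 2.1%.

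Finally, this is a pilot aimed at estimating an effect size. That lessens the weight of any power figure. But the plan states 80% power and a minimum of 1080, and about 6 SCT infants per arm would also weaken the estimation goal.

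**Conclusion.** The concern holds. The 9-month and 5-month statements conflict in the current text, and the planned minimum of 1080 post-period infants depends on the 9 months. With 20 PCPs over 5 months, the range is 600 to 1000: 1080 is never reached, and 1000 only at the top rate. At the minimum rate and 2.1% prevalence, 12.6 SCT infants are expected against 21, and power is below 80% under all five methods, whether the pre-period is 6 months (arcsine 63%) or supplies 1080 infants (71%).

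The effect is confined to the SCT comparison and to statements about each arm separately. The 74- and 43-infant calculations are still met many times over. SCT power is roughly back at its planned level at 9 to 10 infants per PCP per month. All these figures, like the plan's own, ignore clustering by PCP and clinic.

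The General Schema still carries an editing note to replace a 3-month label with a 6-week one. Three 3-month steps make 9 months, so the sample size text may be left over from a longer schedule. That is an inference, and the conclusion does not depend on it.

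**What to change.** 1. Reconcile the 9 months in the Sample Size Justification with the 5 months in Duration of Study Participation.
2. State the record-extraction window for the primary endpoint, before and after the intervention.
3. For those windows and 6 to 10 infants per PCP per month, restate the expected infants per period and per arm, the expected SCT infants, and SCT power with one named test. For 20 PCPs and a 5-month post-period, this means 600 to 1000 infants (300 to 500 per arm) and about 13 to 21 with SCT.
4. If more than 20 PCPs, capture of all infants at a site, or an SCT prevalence above 2.1% is expected, say so and calculate with that figure.
5. If extraction really runs for 9 months, say so in the duration section. Under Infant Identification, add a phase after Intervention C, or state explicitly how infants first seen later are classified.

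The cost is wording in two or three sections and one recalculation, with no new participants or procedures. The drawback is that the stated SCT power becomes less favourable unless a higher rate, more PCPs or a higher prevalence can be justified.
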